 2.0 Final

 Date:
 10 March 2023

 EudraCT No:
 2022-003855-32

7.2. Description of investigational product(s)

Nirmatrelvir, placebo for nirmatrelvir and ritonavir is provided from Pfizer, packed and labelled from Almac Sounderton, Almac Souderton [name], shipped to ApoEx, for storage at room temperature (15 to 30°C).

Ritonavir is manufactured by Hetero Labs Limited under NDC 31722-597-30 (Camber Pharmaceuticals, Inc.).

Possible deficiencies related to the handling, storage and quality of the IMP should be reported to the study monitor and also directly to [contact] and [contact]

7.3. Dose and administration

The safety and tolerability of nirmatrelvir and ritonavir has been extensively studied in preclinical species as well as in humans. Nirmatrelvir/ritonavir 300/100 mg twice daily (q12h) administered orally for 5 days has been approved for the treatment of mild-to-moderate COVID-19 in adults and pediatric patients. Safety data in up to 10 days of dosing was demonstrated in the EPIC-PEP trial [9] [10] The dose to be used in the PROLIFIC trial is the same as approved for treatment in acute COVID-19. The prolonged dosing with 15 days of treatment is deemed necessary to ensure that Nirmatrelvir reaches hypothesized SARS-CoV-2 viral tissue reservoirs.

7.4. Packaging, labeling, and handling of investigational products

Nirmatrelvir will be provided in blister wallets, including 24 tablets. Each wallet will be labeled as required per country requirement, and with blinded labels.

Placebo for nirmatrelvir will be provided in blister wallets, including 24 tablets. Each wallet will be labeled as required per country requirement, and with blinded labels.

Ritonavir will be provided in high density polyethylene (HDPE) bottles, including 12 tablets. Each bottle will be labeled as required per country requirement.

Nirmatrelvir, and placebo for nirmatrelvir, will be provided by Pfizer and distributed via the hospital pharmacy.

Ritonavir will be provided by Pfizer and distributed via the hospital pharmacy.

7.5. Drug accountability and treatment compliance

The patients will be instructed to save empty blisters and bottles and bring unused investigational product for returning to the clinic at next visit after end of treatment. This to check randomization codes on the investigational products versus patient's study code,

 Version No:
 2.0 Final

 Date:
 10 March 2023

 EudraCT No:
 2022-003855-32

check compliance with investigational product intake compared to the self-registered information in patient study diary and to perform drug accountability.

7.6. Randomization

Subjects are included/randomized consecutively, in accordance with a randomization list, as they are found to be eligible for inclusion in the study. Subjects will be assigned a unique identifier, allocated to either Treatment group or Control group in a 2:1 ratio.

If a subject discontinues their study participation, their subject code will not be reused, and the subject will not be allowed to re-enter the study again.

7.7. Blinding

The blinding will be maintained through the Day 90 follow-up visit. Subjects, the sponsor, investigators, monitors, all study site personnel involved in the study, carrying out study procedures, evaluating patients, entering study data, and/or evaluating study data will remain blinded to treatment allocations until all patients have completed the Day 90 follow-up assessments and the database has been locked for the analysis.

Active and placebo products will be of identical appearance.

7.8. Code breaking

Code breaking will be done after end of study and the database is closed.

When a SUSAR occurs for a subject participating in the study, Pfizer will request the unblinding of the treatment assigned. The randomization code will not be communicated to the site staff, to sponsor; unblinded SUSAR information will be provided to Läkemedelsverket (Swedish Medical Product Agency) only. SUSARs will be reported to Etikprövningsmyndigheten in a blinded fashion.

In case of a medical event, that requires medical treatment of a subject and unblinding needs to be done for further medical management, the investigator can unblind the subject by contacting ApoEx. In case of a medical event outside office hours, and the management of which would require knowledge of the blinded treatment assignment, the code can be accessed through ApoEx (assign contact person and 24/7 access email/phone number).

When code breaking is done the subject can continue in the study for follow-up visits, but not on study medication.

7.9. Concomitant medications

Medications that are considered necessary for the safety and well-being of the subject can be given at the discretion of the investigator, unless otherwise specified as an exclusion criterion. Concomitant medications will be reported in the eCRF.

All prescription and over-the-counter medications including vaccines taken by the participant within 30 days before study entry will be recorded.

 Version No:
 2.0 Final

 Date:
 10 March 2023

 EudraCT No:
 2022-003855-32

Concomitant therapies and adjunctive therapeutic procedures will be collected through the Day90 visit and recorded in the eCRF. The data will be collected from study participants as well as through EMRs and national registries e.g., the registry for prescribed drugs.

7.9.1. Prohibited concomitant medication

Information of contraindications and prohibited concomitant medication is stated in the investigator brochure for Nirmatrelvir and for Ritonavir in pdf document "FDA_report_NDC 31722-597-30_March9_2023.pdf"

7.9.2. Contraceptive methods for WOCBP

Methods that can achieve a failure rate of less than 1% per year when used consistently and correctly are considered as highly effective birth control methods [11] [12]

Such methods include:

- combined (estrogen and progestogen containing) hormonal contraception associated with inhibition of ovulation 1:
 - o oral
 - intravaginal
 - o transdermal
- progestogen-only hormonal contraception associated with inhibition of ovulation 1:
 - o oral
 - injectable
 - o implantable 2
- intrauterine device (IUD)²
- intrauterine hormone-releasing system (IUS)²
- bilateral tubal occlusion ²
- vasectomized partner ^{2,3}
- sexual abstinence ⁴

Patients using combined hormonal contraceptives should be advised to use an effective alternative contraceptive method or an additional barrier method of contraception during treatment with nirmatrelvir /ritonavir, and until one menstrual cycle after stopping nirmatrelvir /ritonavir.

7.10. Destruction

The returned unused investigational product will be destroyed by local routines at the hospital's pharmacy, after approval from the monitor.

¹ Hormonal contraception may be susceptible to interaction with the IMP, which may reduce the efficacy of the contraception method

² Contraception methods that in the context of this guidance are considered to have low user dependency.

³ Vasectomized partner is a highly effective birth control method provided that partner is the sole sexual partner of the WOCBP trial participant and that the vasectomized partner has received medical assessment of the surgical success.

⁴ In the context of this guidance sexual abstinence is considered a highly effective method only if defined as refraining from heterosexual intercourse during the entire period of risk associated with the study treatments. The reliability of sexual abstinence needs to be evaluated in relation to the duration of the clinical trial and the preferred and usual lifestyle of the subject.

 Version No:
 2.0 Final

 Date:
 10 March 2023

 EudraCT No:
 2022-003855-32

8. Assessment of endpoints for clinical efficacy, safety, and pharmacodynamics

8.1. Demography

Demographic data consists of age, gender, and ethnicity.

8.2. Medical history

8.2.1. COVID-19 diagnosis

Information on Covid-19 diagnosis and microbiological verification are captured as well as information on vaccination status. Reinfections with Covid-19 are also captured.

8.2.2. Other diagnoses

Other current, chronic or for the study relevant diagnoses, either requiring pharmaceutical treatment or other treatment of importance will be captured.

8.3. Efficacy assessments

8.3.1. Health related quality of life

Patient reported outcomes will be captured through the questionnaires EQ-5D-5L, CAT, Compass 31, FSS, MAPS, MFS, mMRC, MoCa, Nijmegen and PEM which can be found in Appendix B. The questionnaires will be provided digitally or in a paper format, with the option to fill in prior (day before) a visit.

8.3.2. Physical function tests

Physical function tests consist of a 6-minute walk test (6 MWT), hand grip test, accelerometers and test of maximal inspiratory pressure.

The 6 MWT test is conducted on a straight 30-meter track in a corridor. Pulse and oxygen level (SpO2), Borg Cr-10 (breathlessness and leg fatigue) and Borg RPE (perceived exertion) is measured before and after the test. The patient is instructed to walk as far as possible for six minutes. To walk in normal pace to a cone and turn around and continue to walk back and forth for six minutes. If the patient stops during the test they can rest and check SpO2 and heart rate. The patient will be asked for the reason for not completing the assessment. The total distance walked in meters will be recorded.

Hand grip test is measuring the maximum hand strength, where the patient is instructed to hold a grip and press as much as long and as tightly as possible for the best result until the needle on the device stops rising. The patient will start with the right hand and then repeat the measurement with the left hand. Three measurements in kg for each hand, alternating sides will be measured.

Accelerometers is measuring the total volume of physical activity. The accelerometer will be placed on the thigh and must be on for a period up to 7 days. The accelerometer will then be removed by the patient for return to the clinic.

 Version No:
 2.0 Final

 Date:
 10 March 2023

 EudraCT No:
 2022-003855-32

Maximal inspiratory pressure (MIP) is a measure of inspiratory muscle strength. The patient is asked to perform five MIP maneuvers, with a goal of matching the highest two within 10 cmH2O. The patient is in a sitting position. The patient is instructed to exhale slowly and completely, seal lips firmly around the new mouthpiece, and then "breath in hard." and then repeat the maneuver at least 3 times.

8.3.3. Active standing test

Heart rate and blood pressure will be measured after a 10-minute resting period in the supine position and then every minute for 10 minutes after standing up. Heart rate will be measured with continuous ECG and blood pressure manually using an arm cuff. Data collected: Supine heart rate and blood pressure, Maximum heart rate during ten minutes standing, minimum blood pressure during ten minutes standing.

8.3.4. Endothelial function test

Endothelial function will be measured using an EndoPAT device. In short, an arm and finger cuff are attached to the patient and baseline blood pressure is recorded on a beat-to-beat basis while the patient rests in the supine position. The arm cuff in then inflated to 10-20mmHg above patient's systolic blood pressure for five minutes. The arm cuff is then deflated, and the blood pressure is continuously recorded for an additional five minutes. Data collected: Reactive Hyperemia Index (RHI) and Augmentation Index (AI).

8.3.5. Dynamic spirometry

The spirometry test is performed using a spirometer. Spirometry is the most common type of pulmonary function or breathing test. This test measures the air volume when breathing in and out of the lungs, as well as how easily and fast it can be blown out of the lungs. Forced vital capacity, FVC, is the total volume of air exhaled during a rapid exhalation (from maximum inhalation). Forced expiratory volume in one second, FEV1, is the volume of air forced out of the lungs in 1 second. Peak expiratory flow (PEF) is the maximum flow achieved during a forced expiration starting from the level of maximal lung inflation.

8.3.6. ECG

24-hour ECG will be recorded using an ECG-device capable of collecting ECG for at least 24 hours. ECG-data will be stored digitally on an external server. ECG will not be used for patient safety monitoring and will not be reviewed at the time it is recorded. Data collected: Heart Rate Variability, min, max and average heart rate.

8.4. Exploratory efficacy assessments

8.4.1. Plasma protein biomarkers

Plasma protein assessment using Olink Explore panel of plasma cytokines and assessment of circulating spike levels [13] in patients before and after Paxlovid® or placebo treatment. We will also assess circulating nucleosome levels (Histone H3) in circulation as a biomarker of persistent innate immune activation.

8.4.2. Genetics

DNA will be extracted and subjected to genome-wide genotyping using the Illumina OmniExpress array. The data will be used to determine HLA types.

 Version No:
 2.0 Final

 Date:
 10 March 2023

 EudraCT No:
 2022-003855-32

8.4.3. Other biomarkers

Bulk mRNA sequencing from PaxGene stabilized samples, batch combined from the same individuals and randomized across treatment groups to capture genome-wide transcriptional alterations in response to active treatment vs placebo. (Such analyses will also take cell composition into account to assess transcriptional changes not only explained by changes in cell composition.)

Single cell sequencing of VDJ + mRNA from sorted memory T-cells using BD Rhapsody platform will pe performed to assess T cell functional state and clonal expansion as a test of superantigen mediated activation.

8.5. Safety assessments

8.5.1. Laboratory safety assessments

Hematology, biochemistry, coagulation, and other analyses will be analyzed at the Hospital Laboratory at Karolinska University Hospital, Solna. The timepoints are summarized in Table 1, Schedule of assessments. The hospital regularly reviews reference values for each of the biomarkers and the reference values are provided by the hospital lab upon delivering lab results. The reference values serve as guidance for the clinician and study team, who will judge whether a value outside of the reference value is clinically significant or not.

Hematology	Chemistry	Other
Hemoglobin	BUN or urea	Ferritin
Hematocrit	Creatinine or Cystatin-C to	Procalcitonin
RBC count	enable eGFR calculation	
Platelet count	using CKD-Epi or CKD-	Haptoglobin
WBC count	EpiCysC	
Total neutrophils (Abs)	Glucose	Thyroid function
Eosinophils (Abs)	Calcium	TSH
Monocytes (Abs)	Sodium	T4 (free)
Basophils (Abs)	Potassium	
Lymphocytes (Abs)	Chloride	Coagulation
	Total CO₂ (bicarbonate)	PT/aPTT
	AST, ALT	Fibrinogen
	Total bilirubin	D-dimer
	Albumin	
	Total protein	HIV test
	NT-proBNP	Pregnancy test (βhCG)¹
	LDH	
	hsCRP	
	ESR	

¹ A negative urine or serum (β-hCG) pregnancy test must be confirmed at screening for WOCBP only. Pregnancy tests will also be done whenever 1 menstrual cycle is missed during the active treatment period (or when potential pregnancy is otherwise suspected) and at Day 15 or ET visit.

The rapid antigen test will be evaluated directly at the clinic after testing.

8.5.2. Vital signs

Vital signs consist of blood pressure, heart rate, respiratory rate, body temperature and is measured as summarized in Table 1 "Schedule of assessments".

 Version No:
 2.0 Final

 Date:
 10 March 2023

 EudraCT No:
 2022-003855-32

8.5.3. Physical examination and anthropometry

A physical examination will be performed by a physician and will include examination of the following: general appearance, eyes, ears, nose, throat, chest/respiratory, heart/cardiovascular, gastrointestinal/liver, musculoskeletal/extremities, dermatological/skin, thyroid/neck, lymph nodes, and neurological. Each component will be recorded as "normal" or "abnormal" at each visit. Abnormalities should be described.

Weight and height are assessed at screening, where height may be self-reported.

8.6. Adverse Events

8.6.1. Definitions

Adverse Event (AE): Any untoward medical occurrence in a clinical investigation subject administered a medicinal product and, which does not necessarily have a causal relationship with the treatment, can be an unfavorable and unintended sign (including an abnormal laboratory discovery), symptom or disease temporally associated with the use of the medicinal (investigational) product, whether related to the medicinal (investigational) product or not.

Serious adverse event (SAE): Any untoward medical occurrence that at any dose:

- results in death
- is life-threatening
- requires inpatient hospitalization or prolongation of existing hospitalization
- results in persistent or significant disability or incapacity
- results in a congenital anomaly/malformation

Medical and scientific assessment will be made to determine if an event is "serious" and whether it would prompt reporting in other situations, for example important medical events that may not be directly life-threatening or result in death or hospitalization but may compromise the study subject or may require intervention to prevent one of the other results set forth in the definitions above. These should also normally be considered as SAEs.

Suspected Unexpected Serious Adverse Reaction (SUSAR)

A SUSAR is a reaction/event that is unexpected, serious, and suspected to be caused by the treatment, i.e., adverse events that are not included in the Investigator's Brochure (IB) or SPC.

8.6.2. Assessment of Adverse Events

Assessment of causal relationship

The investigator is responsible for determining whether there is a causal relationship between the AE/SAE and use of the investigational product.

 Version No:
 2.0 Final

 Date:
 10 March 2023

 EudraCT No:
 2022-003855-32

Those AEs which are suspected of having a relationship to the investigational product will be followed up until the subject has recovered or is well taken care of and on their way to good recovery (see also section **Follow-up of Adverse Events**).

All AE will be categorized either as likely related, possibly related, or not related, in accordance with the definitions below:

Likely related: Clinical event, including abnormal results from laboratory analyses, occurring within a reasonable time after administration of the intervention/investigational product. It is unlikely that the event can be attributed to underlying disease or other medications but is most likely caused by the investigational product and its emergence is reasonable in relationship with use of the investigational product.

Possibly related: Clinical events, including abnormal results from laboratory analyses, occurring within a reasonable time after administration of the intervention/investigational product. The event could be explained by the investigational product and its emergence is reasonable in relationship with use of the investigational product, but there is insufficient information to determine the relationship. The event could be explained by an underlying disease or other medications.

Not related: Clinical event, including abnormal results from laboratory analyses, that is not reasonably related to the use of the intervention/investigational product. The event is unlikely related to the intervention/investigational product and can be explained by other medications or underlying disease.

Assessment of intensity

Each adverse event shall be classified by an investigator as mild, moderate or severe.

Mild: The adverse event is relatively tolerable and transient in nature but does not affect the subject's normal life.

Moderate: The adverse event causes deterioration of function but does not affect health. The event can be sufficiently unpleasant and interferes with normal activities but does not completely obstruct them.

Severe: The adverse event causes deterioration of function or work ability or poses a health risk to the subject.

Assessment of seriousness

The investigator is responsible for assessing the seriousness (serious or non-serious). If the incident is considered serious, this should be reported as a serious adverse event (SAE) by the investigator to Pfizer, with a copy to sponsor (see also section Reporting of Serious Adverse Events (SAE) to Pfizer.

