6.2. Inclusion criteria

To be included in the study, subjects must meet the following criteria:

- 1. The subject has given written consent to participate in the study.
- 2. ≥18 years of age at the time of the Screening Visit
- 3. Post-acute COVID-19 syndrome (PACS) according to the WHO definition
- 4. EQ-5D-5L VAS< 50

 Version No:

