 2.0 Final

 Date:
 10 March 2023

 EudraCT No:
 2022-003855-32

by the subject will be registered in the eCRF regardless of whether they are related to the investigational product or not. Assessment of causal relationship, severity, and whether the AE is considered to be an SAE or not will be done by the investigator directly in eCRF. At minimum, for each AE/SAE, a description of the event is recorded (diagnosis/symptom if diagnosis is missing), start and stop dates, causal relationship, severity, if the AE is considered to be an SAE or not, measures and outcome.

Reporting of Adverse Events (AE)

All AEs shall be registered in the eCRF within 3 working days.

Reporting of Serious Adverse Events (SAE) to Pfizer

Serious adverse events (SAE) are reported to Pfizer, in a protected email with copy to sponsor, on a designated SAE form within 24 hours from when the information received.

For life-threatening events or death, submit the SAE form immediately.

Follow-up information describing the outcome and handling of the SAE is reported as soon as this information is available and not later than 24 hours from when the information is received. The original should be kept in the Investigator Site File.

In addition, SAEs that occur after completion of the active reporting time period as defined above are reportable to Pfizer if the investigator suspects a causal relationship between the Pfizer product and the SAE.

Reporting of potential cases of Drug-Induced Liver Injury (DILI), Assessed Based on Hy's Law criteria

For investigational (non-authorized) medicinal products that are investigational in the United States (irrespective of being authorized elsewhere), interventional clinical study reports with elevations in aspartate aminotransferase (AST) and/or alanine aminotransferase (ALT) in addition to and/or preceding total bilirubin (TBili) elevations (>2 x ULN) are considered potential DILI- (assessed per Hy's law criteria) cases and should always be considered important medical events, even before all other possible causes of liver injury have been excluded.

The threshold of laboratory abnormalities for a potential DILI case depends on the subject's individual baseline values and underlying conditions. Subjects who present with the following laboratory abnormalities should be evaluated further as potential DILI (Hy's law) cases to definitively determine the etiology of the abnormal laboratory values:

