10.3. Descriptive

Descriptive statistics for all efficacy and safety (AE related variables) endpoints by treatment group and visit will be provided.

The number of participants screened will be reported. The number of participants randomized to the double-blind treatment phase, completing the study drug administration, completing the study, and discontinued the study will be summarized from the FAS analysis set for each treatment group.

Baseline demographic and other characteristics will be tabulated for the FAS analysis set and summarized by treatment group. Continuous variables will be described by standard descriptive statistics (mean, standard deviation, median, interquartile range, minimum, and maximum), and categorical variables will be summarized by frequency tables with number and proportion in each category (with the corresponding sample sizes).

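### The Moderate and Severe intensity grades in Protocol 8.6.2 are not mutually exclusive, so the moderate/severe split of adverse events depends on how the grader reads them

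*Protocol*

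**What the plan says.** Under Assessment of intensity, Section 8.6.2 states: "Each adverse event shall be classified by an investigator as mild, moderate or severe". The three grades are then defined.

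- **Mild:** "Mild: The adverse event is relatively tolerable and transient in nature but does not affect the subject's normal life".
- **Moderate:** "Moderate: The adverse event causes deterioration of function but does not affect health". A second sentence adds that such an event "interferes with normal activities but does not completely obstruct them".
- **Severe:** "Severe: The adverse event causes deterioration of function or work ability or poses a health risk to the subject".

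Section 8.6.3 makes severity part of the minimum record for each event and leaves the judgement to the investigator: "causal relationship, severity, and whether the AE is considered to be an SAE or not will be done by the investigator directly in eCRF". Section 10.3 then commits to using the data: "Descriptive statistics for all efficacy and safety (AE related variables) endpoints by treatment group and visit will be provided".

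The protocol has no rule for an event that fits two grades, and it names no other intensity scale.

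**The concern.** An ordered three-grade scale works only if each event has one right place on it. Here the feature that defines Moderate, loss of function, is also listed as sufficient for Severe. The second Moderate sentence suggests that complete obstruction of activities was meant as the upper limit of that grade, but the Severe definition does not mention obstruction.

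Take an event that reduces a participant's activity for two days with no effect on health and without stopping activity altogether. One investigator may record it as Moderate because the Moderate text describes it closely. Another may record it as Severe because function deteriorated. Both have complied with the protocol.

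What is at stake is how the moderate and severe counts in the safety tables can be read. The course lasts 15 days, and the safety experience cited in Sections 2.3, 3 and 7.3 extends to 10 days, so a clear description of tolerability is useful. An analysis plan cannot repair this later, because the grade is fixed when the investigator enters it.

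**Working it through.** No sample size, power or event count enters this point. The check is whether the definitions, written as logical conditions, can both be true of one event.

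**Attributes, all from 8.6.2**

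- F: function deteriorates.
- W: work ability deteriorates.
- H: health is affected or at risk. Treating the Moderate phrase on health and the Severe phrase on health risk as one attribute is an assumption, tested below.
- O: normal activities are completely obstructed.

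**Definitions as written**

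- Moderate = F and not H and not O.
- Severe = F or W or H.

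Moderate also mentions interference with normal activities. It is taken here to accompany F. Making it a separate condition would only narrow Moderate and could not move it outside Severe.

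**Enumeration**

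Four yes/no attributes give 2 × 2 × 2 × 2 = 16 combinations.

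| Set | Condition | Combinations |
|---|---|---|
| Moderate | F=1, H=0, O=0, W either | 2 |
| Severe | all except F=W=H=0 (O either) | 16 − 2 = 14 |
| Both | Moderate combinations that also meet Severe | 2 of 2 |
| Function loss, health unaffected | F=1, H=0, with W and O either | 4 |
| – of these, both grades | O=0 | 2 |
| – of these, Severe only | O=1 | 2 |

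Moderate lies wholly inside Severe.

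**Does the assumption on H matter?** No. If an effect on health and a risk to health are kept apart, Moderate still requires F, and F alone still meets Severe.

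**Effect on the counts.** Let m be the number of events that meet both grades and s the number that meet Severe only. Depending on the reading, the same data give between s and s + m severe events, and between m and 0 moderate events. The protocol gives neither m nor s, so no percentage can be attached.

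**Would exclusive wording work?** Suppose complete obstruction or a health risk is the core of Severe. There are then two options for work ability.

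| Option | Severe | Moderate | Both | Neither |
|---|---|---|---|---|
| Reduced work ability stays Severe | O or H or W: 16 − 2 = 14 | F only: 1 | 0 | 1 |
| Reduced work ability short of complete obstruction is Moderate | O or H: 16 − 4 = 12 | F or W, with H=0 and O=0: 3 | 0 | 1 |

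In both options the overlap is gone, and the one combination left over has no effect of any kind, which is where Mild belongs. The options differ only in where W goes.

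**The case against.** The case for leaving the text alone has several parts.

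*The category is usable.* On an ordered scale an investigator can pick the more specific description, and Moderate is the more specific one. This is fair, and it rules out the inference that Moderate is empty if read literally. Moderate would empty only under a rule to take the higher grade, and the protocol has none. It also has no rule to take the more specific grade, so the ambiguity stands.

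*The overlap has limits.* A reader might infer that any loss of function without a health risk meets both grades. It does not: an event that completely obstructs normal activities is excluded from Moderate and is Severe only.

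*Little depends on intensity.* Section 8.6.2 attaches no action to the intensity grade. Seriousness has its own criteria in 8.6.1, and potential liver injury has laboratory thresholds in 8.6.3. For adverse event variables Section 10.3 promises description, and the test for categorical variables in 10.4 is generic and names no severity comparison. The Safety Monitoring Committee works to a charter that is not shown, so nothing shows that it relies on these grades. Causality, SAEs, laboratory values, vital signs and completion of study drug are also recorded. All of this stands and keeps the issue small.

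*The design limits the harm.* The trial is single-centre (5.1) and investigators stay blinded until database lock (7.7). Inconsistent reading then affects both arms alike. This stands too: it may blur a true difference in severity, but it does not by itself favour an arm.

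**Conclusion.** The point holds as a minor drafting fault. The two definitions overlap: an event with loss of function, no effect on health and no complete obstruction of activities meets both, and nothing in the protocol settles which grade applies. This is a rule stated faultily, not a detail left for later, because exact compliance permits two different answers.

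The consequence is grader-dependent noise in the moderate and severe counts. That conclusion rests on blinding being maintained and on one centre doing the grading. SAE reporting and the primary endpoint are not touched.

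Two stronger readings are not supported. One is that most non-mild events must fall in the overlap because participants enter with "EQ-5D-5L VAS< 50". That criterion describes health at entry and says nothing about the severity mix of new events. The other is a numerical range for the proportion graded severe. Any such range would come entirely from an assumed mix of events, since the protocol gives none.

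**What to change.** Reword the Moderate and Severe definitions in 8.6.2 before grading starts, so that no event can meet both. One way is to reserve Severe for events that completely obstruct normal activities or pose a health risk, and to keep Moderate for loss of function short of that with health unaffected.

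This wording makes one choice that the sponsor must state openly. As now written, reduced work ability of any degree is sufficient for Severe, and the obstruction limit appears only under Moderate and refers to normal activities. The sponsor must say whether reduced work ability short of complete obstruction stays Severe or moves to Moderate. Moving it raises the threshold for Severe and is a change to the scale, not only a clarification. Either choice gives exclusive grades.

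Mirror the final text in the eCRF completion guide. If events have already been graded, regrade them once under the new wording, blinded to allocation. The cost is two sentences in the protocol, a matching edit to the guide and possibly that one regrade. No extra visits or participants are needed.
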